The Whole-Organ Magnetic Resonance Imaging Score (WORMS) in patients with knee OA provides multi-feature, whole-organ assessment of the knee in OA using conventional magnetic resonance imaging (MRI), and shows high inter-observer agreement among trained readers [17]. Whole-organ assessment could help discriminate different patterns of intra-articular involvement in OA; detect early, potentially preclinical, stages of OA;

CONFIDENTIAL

identify structural risk factors for developing clinical OA; or increase scope and sensitivity to change for monitoring disease progression and treatment response in patients with established OA. It takes into account a variety of features that are currently believed to be relevant to the functional integrity of the knee and/or potentially involved in the pathophysiology of OA. It scores each of these features with a sufficient number of increments to allow detection of what are speculated to be clinically relevant changes.

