Potential adverse events associated with MRI knee:

- Discomfort (possible)
- Anxiety or claustrophobia (less possible)
- Peripheral nerve stimulation causing tingling or twitching (rare)
- Injury and burns related to metals (very rare, particularly with the MR screening performed prior to entering MR zone and subjects with contraindications to MR will be excluded from the study)
- Pacemaker dysfunction (very rare; subjects with pacemakers will be excluded from the study)
- Skin burns (very rare)
- Tinnitus and hearing loss (very rare)
- Quench (very rare)

Potential adverse events associated with moderate sedation during procedure:

- Over sedation (less possible)
- Nausea, vomiting, and/or allergic reaction to medications / anaphylaxis (rare)
- Respiratory failure, myocardial infarction, and death (rare)

Potential risks associated with study enrollment and ancillary study procedures:

- Discomfort due to blood draws required for the study (possible)
- Minor local discomfort due to the pressure of the ultrasound transducer on the skin during arterial access (possible)
- Inconvenience at having to return for follow-up visits (possible)
- Discomfort, Thrombophlebitis, bruising, bleeding, blood clot, presyncope or syncope (i.e. fainting) due to blood draws required for the study (less possible)
- Psychological discomfort from clinical trial enrollment and completing study questionnaires (less possible)
- Infection from blood draw for lab tests (rare)
- Loss of confidentiality of medical records (rare)

Risk minimization:

The GAE procedure will be performed by fellowship-trained interventional radiologists who have expertise in endovascular techniques, particularly in selective catheterization and transcatheter embolization techniques.

CONFIDENTIAL

Analgesia during the procedures will be provided using conscious sedation if subject opted to receive conscious sedation. The risks of conscious sedation will be minimized by continuous monitoring of heart rate, blood pressure, oxygen saturation, and cardiac rhythm.

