3.2 Secondary Objectives

The secondary objectives of the study are to determine whether genicular artery embolization is effective in improving

1. Knee pain using an electronic VAS at 1-, 3-, and 12-months (and final 18-48 months visit) post intervention
2. Knee pain using WOMAN pain score at 1- and 12-months (and final 18-48 months visit) post intervention
3. Knee stiffness using the WOMAC knee stiffness score at 1-, 3-, and 12- months (and final 18-48 months visit) post intervention
4. Physical function using the WOMAC function score at 1-, 3-, and 12- months (and final 18-48 months visit) post intervention
5. Self-reported quality of life using EQ-5D-5L scale at 1-, 3-, and 12- months (and final 18-48 months visit) post intervention [28]
6. Synovitis on MRI at 3 months post intervention

Other secondary objectives are to assess

1. Feasibility / technical success defined as successful selective catheterization of target vessel(s) and embolization from at least one feeding artery of the knee joint (with the embolization endpoint defined as suppression or reduction in the filling of (and therefore blood flow in) abnormal vessels visible on angiography).
2. Reduction in frequency of pain medication usage over 30-day period assessed at baseline and at 1, 3, and 12 months follow-up visits post intervention (acetaminophen, over the counter NSAIDs, prescription NSAIDs, opioids)
3. Reduction in frequency of knee injection therapy over 12-month period (assessed at baseline and at 12-month follow-up visit post intervention)
4. Reduction in frequency of need for physical therapy over 12-month period (assessed at baseline and at 12-month follow-up visit post intervention)
5. Safety evaluated by cumulative rates of adverse events (AE), as well as type and severity of each adverse event.

4 Study Design and Endpoints

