4.2.2 Secondary Study Endpoints Analysis

Secondary efficacy endpoints are:

- 1- WOMAC pain score at 1- and 12- months (and final 18-48 months visit) post intervention
- 2- Pain electronic VAS at 1-, 3-, and 12- months (and final 18-48 months visit) post intervention
- 3- Knee stiffness WOMAC score at 1-,3-, and 12- months (and final 18-48 months visit) post intervention
- 4- Physical function WOMAC score at 1-, 3-, and 12- months (and final 18-48 months visit) post intervention
- 5- Total WOMAC score at 1-,3-, and 12- months post intervention
- 6- Self-reported quality of life using EQ-5D-5L scale at 1-, 3-, and 12- months (and final 18-48 months visit) post intervention.
- 7- MRI findings at 3- months post intervention
- 8- Pain medication usage at 1-, 3-, and 12- months (and final 18-48 months visit) post intervention
- 9- Injection therapy requirements (hyaluronic acid or steroid) at 12- months (and final 18-48 months visit) post intervention
- 10- Physical therapy requirements at 12- months (and final 18-48 months visit) post intervention
- 11- Feasibility / technical success
- 12- Laboratory findings at 1-, 3-, and 6- months (and final 18-48 months visit) post intervention

Secondary safety endpoints are:

- 13- Number/rate, severity, and description of complications, adverse events, or poor outcomes that are secondary to the procedure, which will be summarized using counts and simple statistics (i.e., mean number of patients with complications.)

CONFIDENTIAL

5 Study Enrollment and Withdrawal

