7.1 Study Procedures/Evaluations

7.1.1 Study Specific Procedures

- Medical history
 - Complete medical history will be obtained from medical records if available and/or by interview during clinic visits.
- History of previous and concomitant treatment
 - Knee injections and frequency over the 12 months
 - Medication history over the last month will be obtained during pre and post intervention study visits. Medication history will focus on medications currently taken for the treatment of knee OA; including prescription and over-the-counter medications for pain.
 - Physical therapy and frequency over the 12 months
 - Weight loss / gain
- Focused physical examination:
 - Vital signs (temperature, blood pressure, heart rate, oxygen saturation, height, weight, BMI)
 - Focused knee examination.
 - Lower extremity pulses
- Imaging assessment with knee MRI
 - Baseline and follow-up (at 3 months) knee MRI will be performed.
 - Knee MRI protocol will include: Axial t2 FS, Sagittal PD, Sagittal T2 FS, Coronal PD FS, Coronal PD FS, non-contrast axial and sagittal T1 FS.
 - Imaging variables collected for this study is found in the attached eCRFs
- A discussion of the results of any study specific procedures (e.g., radiographic or other imaging or laboratory evaluations) will be provided to participant after the completion of the study unless these information represent a significant health-related issue.
- Laboratory tests:
 - Baseline and follow-up (at 1-, 3-, and 12-, 18-48 months) laboratory tests will be obtained
- Administration of questionnaires or other instruments for patient-reported outcomes:
 - Electronic VAS
 - KOOS questionnaire
 - Self-reported quality of life EQ-5D-5L questionnaire

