10.4.3 Analysis of the Secondary Endpoint(s)

Analysis of secondary endpoints include: (1) changes in the mean WOMAC and VAS pain scores, the mean WOMAC knee stiffness and physical function scores and the total WOMAC knee physical function score; (2) the technical success rate (defined as the proportion of patients for whom the procedure was successfully completed); (3) the adverse event rate (defined as the proportion of patients showing each type of adverse event or any adverse event); (4) reduction in the usage of pain medication, the frequency of infection therapy, the need for physical therapy; and (5) the proportion of patients showing synovial thickening, joint effusion, meniscus tear, synovial enhancement, osteophytes. A point estimate and 95% confidence interval will be provided for each secondary outcome at each time and for the change in each outcome from baseline to each post-treatment follow-up visit. Changes in the outcomes from baseline to follow-up will be tested using the paired-sample Wilcoxon signed rank test for the WOMAC and VAS scores and the McNemar test for the other measures which will be assessed as binary outcomes (e.g., whether or not the patient reported usage of pain medication on a daily basis).

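### Section 10.4.3 plans to analyse synovial enhancement, which the non-contrast MRI protocol cannot show, and leaves the synovitis objective to an insensitive present/absent test

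*Combined protocol and SAP*

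**What the plan says.** Section 3.2 lists, as the sixth secondary efficacy objective, "Synovitis on MRI at 3 months post intervention". Section 4.2.2 states the matching endpoint only as "MRI findings at 3- months post intervention", with no definition of synovitis and no score.

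Section 10.4.3 turns this into five features: "the proportion of patients showing synovial thickening, joint effusion, meniscus tear, synovial enhancement, osteophytes". Each gets a point estimate and a 95% confidence interval. The Wilcoxon signed-rank test is reserved for the WOMAC and VAS scores, with "the McNemar test for the other measures which will be assessed as binary outcomes".

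Section 7.1.1 gives the MRI acquisition: axial and sagittal T2 FS, sagittal PD, then "Coronal PD FS, Coronal PD FS, non-contrast axial and sagittal T1 FS". It refers to the eCRF for the imaging variables.

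Section 2.1 describes a graded whole-organ MRI score for conventional MRI and says of it: "It scores each of these features with a sufficient number of increments to allow detection of what are speculated to be clinically relevant changes". No objective, endpoint or analysis section takes it up.

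**The concern.** There are two separate problems.

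The first is a contradiction. Enhancement is the uptake of a contrast agent, so it cannot be read from scans made without one. A planned outcome has no planned acquisition. If the field is left blank, the outcome is missing for everyone. If the reader enters absent at both visits, the table will show no enhancement before or after treatment, and a reader could take that as a finding.

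The second is loss of information. The plan does not say which of the five features decides the synovitis objective. Those that bear on synovitis and can be read without contrast are scored present or absent. A patient whose synovitis shrinks but does not disappear counts as unchanged.

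Section 2.4.2 lists synovitis reduction as a potential benefit, so a real change could go undetected. Section 10.1 says that no formal SAP will be written, which makes 10.4.3 the only place to correct this.

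**Working it through.** **Plan's own figure.** No power or sample size is given for MRI. The only design figure concerns the primary endpoint (section 10.5: 23 patients, 80.4% power, level 0.047; section 10.2: at least 16 responders). It reproduces: P(X ≥ 16 | n = 23, p = 0.5) = 0.0466 and P(X ≥ 16 | n = 23, p = 0.75) = 0.8037. It does not bear on the MRI endpoint.

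**Step 1: sequences against outcomes.** Every listed sequence is T2 FS, PD, PD FS or T1 FS, and the T1 entry reads "non-contrast axial and sagittal T1 FS". The list in section 2.4.1 under "Potential adverse events associated with MRI knee" covers discomfort, claustrophobia, burns and similar. It names no contrast-agent risk, although the angiography list in the same section does cover iodinated contrast. The two places agree that the MRI is unenhanced; section 10.4.3 does not fit them.

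**Step 2: the enhancement test.** If the feature is recorded absent at both visits, there are 0 discordant pairs and McNemar gives p = 1, whatever happened in the joint.

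**Step 3: what McNemar needs.** The exact two-sided p-value when all m discordant patients change in one direction is 2 × 0.5^m. For m = 5 this is 0.0625; for m = 6 it is 0.031. So at least 6 one-way changes are needed. With 40 pairs (the planned number with data) and an assumed 5% going from absent to present, exact power is:
- 0.17 if 15% go from present to absent
- 0.36 if 20%
- 0.57 if 25%
- 0.74 if 30%
- 0.94 if 40%

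The test can be done, but it needs a large change.

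**Step 4: graded against present/absent.** The assumptions, none from the documents, are 40 pairs, an underlying bivariate normal severity with correlation 0.5, and a two-sided 5% level. The grade cuts this severity into three or four levels. The binary feature cuts it once, either at the baseline median (50% have it at baseline) or 1 SD above the mean (16% have it). For a shift of 0.5 SD:
- Median cut: P(present to absent) = 0.273, P(absent to present) = 0.082, exact McNemar power 0.446.
- Cut at +1 SD: 0.126 and 0.034, power 0.156.

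The Wilcoxon figures are simulated. The McNemar ranges span simulation and exact calculation.

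| True shift | Wilcoxon, 3- or 4-level grade | McNemar, median cut | McNemar, +1 SD cut |
|---|---|---|---|
| 0.3 SD | 0.30–0.36 | 0.16–0.17 | 0.07–0.08 |
| 0.5 SD | 0.65–0.76 | 0.44–0.45 | 0.15–0.16 |
| 0.8 SD | 0.95–0.99 | 0.85–0.86 | 0.31–0.33 |

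At 0.5 SD, a four-level grade with symmetric cuts gives about 0.76, a three-level grade about 0.70, and a four-level grade with most patients in the lowest grades about 0.65. A more lopsided grade would give less, so the range is not a lower bound. Treating severity as fully continuous would give about 0.86, but no graded MRI item has that resolution.

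**The case against.** A reader might infer that the synovitis analysis depends on enhancement and that the objective therefore cannot be answered. The documents do not support that. Enhancement is one of five features. Synovial thickening and joint effusion do not need contrast, both bear on synovitis, and each gets an estimate, an interval and a paired test.

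It can also be said that the whole-organ score appears only as background, that the trial is a single-arm pilot with many secondary endpoints and no MRI power target, and that a graded score is a design preference. That is partly fair: nothing obliges the investigators to use that score. Meniscus tear and osteophytes are not out of place either, since the endpoint is worded broadly and the plan nowhere calls them measures of synovitis.

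The size of the gain depends on the assumed shift. At 0.8 SD a median-cut McNemar test already reaches about 0.85, which leaves little to recover.

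Finally, section 7.1.1 sends the reader to eCRF imaging fields that are not in the supplied text, so graded readings may already be collected. If so, section 10.4.3 still does not analyse them.

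What stands is the mismatch between 7.1.1 and 10.4.3, the absence of a named measure for the objective, and the blindness of a present/absent analysis to partial improvement.

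**Conclusion.** The point holds in this form. Synovial enhancement cannot be assessed with the listed MRI protocol and should not be an outcome. The synovitis objective remains answerable, but only weakly, because the usable features are dichotomised and none is named as decisive.

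The contradiction follows from the text alone and needs no assumption beyond what enhancement means. The loss of power is conditional: at an assumed shift of 0.5 SD it is roughly 0.65–0.76 against 0.44 or 0.15, and across shifts of 0.3 to 0.8 SD the grade stays ahead by a varying margin. Those figures rest on the assumed normal severity, correlation 0.5, the cut-points and 40 complete pairs. This is a secondary endpoint, so the change is worth making but does not affect the primary conclusion.

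**What to change.** 1. Delete synovial enhancement from section 10.4.3, so that it agrees with the non-contrast acquisition in 7.1.1.
2. In sections 3.2, 4.2.2 and 10.4.3, name one graded synovitis/effusion measure as the outcome for the sixth objective. That item of the whole-organ score described in section 2.1 is one example.
3. Have the study's existing musculoskeletal radiologist read it from the non-contrast sequences, masked to time order. The study is open label (4.1), and masked reading is stated only for the radiographic grade (7.1.2).
4. Test the baseline to 3-month change with the paired Wilcoxon signed-rank test, and report the other MRI findings as descriptive proportions.
5. The Schedule of Activities (note 1) and section 7.3.2 allow a pre-existing MRI as baseline. Flag patients whose earlier scan used different sequences.

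The cost is wording, slightly longer reading time and, if the eCRF does not already hold it, one graded field. No further scan, visit or patient is needed.

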7.2 Laboratory Procedures/Evaluations

7.2.1 Laboratory Evaluations

Baseline laboratory tests on peripheral venous blood drawn from patient during clinic visit #2 (if not available within the last 30 days prior to procedure.

- **Hematology:** Complete blood count (CBC)
- **Biochemistry:** Basic metabolic panel (BMP)
- **Coagulation profile:** INR
- **Pregnancy test:** point pregnancy test will be performed prior to procedure as standard procedure prior to fluoroscopic examination.

Baseline and follow-up laboratory tests on urine samples and peripheral venous blood drawn from patient during clinic visits (2, 5, 6, 7). Approximately 10 cc of blood will be collected from peripheral venous blood in each visit that requires collection of blood samples.

- **Inflammatory biomarkers:**
 - IL-6,
 - MMP (total activity assay),
 - IL1Ra,
 - sRAGE,
 - hsCRP,
 - VEGF,
 - S100 protein
- **Pain biomarkers**
 - Substance P
 - NGFb,
 - CCL2
- **Matrix degradation collagen biomarkers**
 - CTX-II and CTX-I.
- Type IV collagen markers (C4M, PRO-C4)*
- PRO-C6 measuring endothelium dysfunction*
- Synovial and cartilage markers (C2M, ARGS, CRPM, C1M, C3M)*

The current approved IRB protocol involves collection of blood and urine from all subjects at baseline, 1-month, 3-month, and 12-month follow up to analyze multiple serum, urine, and plasma biomarkers. We are requesting IRB modification to add an optional final visit for patients who completed 12 months follow up by August 31, 2024 after obtaining informed consent. This visit will include blood and urine collection similar to prior visits. No significant increase in risk. At the patient's request, this visit can be performed by a telemedicine visit, a phone call, or via a secure email to participant. In this case, the informed consent can be obtained via phone and the coordinator / investigator will sign in the presence of a witness. If the visit is performed via telemedicine or phone call, the research coordinator will ask the patient the questions and document the answers. If performed via email, the coordinator will send the questionnaire to patient using a secure email (sendsafe) and participants can email it back to

CONFIDENTIAL

This material is the property of the NYU School of Medicine and Langone Medical Center. Do not disclose or use except as authorized in writing by the study sponsor
Interventional Template Version: 12 February 2020

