10.5 Sample Size

The sample size was initially selected based on primary objective so that the study will have 80% power at the 5% significance level for testing the null hypothesis H_0 : $PT \leq 0.5$ against the alternative hypothesis H_A : $PT \geq 0.75$, where PT is the true proportion of patients that will manifest a positive treatment response. As a result, the study will accrue 23 patients since this sample size will endow the test with 80.4% power at a realized significance level of 0.047. with 20% attrition, the study will need 29 patients. We are requesting increase in the sample size to 40. With 20% with 20% attrition, the study will need to enroll 50 patients. The PI and sub-investigators determined that increase in the sample size is necessary to

CONFIDENTIAL

evaluate the role of GAE as a disease-modifying treatment option for knee OA. Since this current study is the only active study in the U.S collecting samples for biomarker analysis and the need for a larger sample size to evaluate changes in biomarker levels, an increase in sample size is needed.

11 Source Documents and Access to Source Data/Documents

Source data is all information, original records of clinical findings, observations, or other activities in a clinical trial necessary for the reconstruction and evaluation of the trial. Source data are contained in source documents. Examples of these original documents, and data records include: hospital records, clinical and office charts, laboratory notes, memoranda, subjects' diaries or evaluation checklists, pharmacy dispensing records, recorded data from automated instruments, copies or transcriptions certified after verification as being accurate and complete, microfiches, photographic negatives, microfilm or magnetic media, x-rays, subject files, and records kept at the pharmacy, at the laboratories, and at medical-technical departments involved in the clinical trial. It is acceptable to use CRFs as source documents. Data collected on electronic CRFs using TrialMaster are attached to this protocol (see attachment 4).

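### Section 10.4.3 tests medication, injection and physical-therapy frequencies as yes/no outcomes and names no test for EQ-5D-5L or the biomarkers; section 4.2.2 item 12 sets laboratory findings at a 6-month visit that does not exist

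*Combined protocol and SAP*

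**What the plan says.** Section 10.4.3 of the combined protocol and SAP names two tests for change from baseline. The first is the "paired-sample Wilcoxon signed rank test for the WOMAC and VAS scores". The second is "the McNemar test for the other measures which will be assessed as binary outcomes". The only coding offered as an example is "whether or not the patient reported usage of pain medication on a daily basis".

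The same section lists five groups of secondary analyses: WOMAC and VAS scores; technical success; adverse events; use of pain medication, injections (printed there as infection therapy) and physical therapy; and MRI features. It also promises estimation: "A point estimate and 95% confidence interval will be provided for each secondary outcome at each time and for the change in each outcome". No scale or interval method is given.

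Section 3.2 words the medication objective as "Reduction in frequency of pain medication usage over 30-day period assessed at baseline and at 1, 3, and 12 months follow-up visits". The injection and physical-therapy objectives are likewise reductions in frequency, over 12 months.

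Section 4.2.2 lists EQ-5D-5L (item 6) and, as item 12, "Laboratory findings at 1-, 3-, and 6- months (and final 18-48 months visit) post intervention". Section 7.2.1 describes "collection of blood and urine from all subjects at baseline, 1-month, 3-month, and 12-month follow up".

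Section 10.5 enlarges the trial from 23 to 40 evaluable patients. It gives two reasons: the question of a disease-modifying role, and "the need for a larger sample size to evaluate changes in biomarker levels, an increase in sample size is needed". Section 10.1 says that no formal SAP will precede database lock, so no later document is planned to fill gaps in 10.4.3.

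**The concern.** There are three linked problems.

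- **Test and objective do not match.** A frequency is reduced to yes/no. With the one coding given, a patient who goes from 25 analgesic days in 30 to 3 counts as unchanged, because neither value is daily use. A patient who skips a single day after daily use counts as improved.
- **Two endpoints have no test.** EQ-5D-5L and the biomarkers appear nowhere in the 10.4.3 list. The biomarkers helped to justify treating 17 more evaluable patients with an invasive procedure, so their analysis should be written down before the data are seen.
- **One laboratory time point cannot be observed.** Item 12 asks for 6 months, and the 12-month samples belong to no endpoint.

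At stake are the power and interpretability of the secondary results, and the freedom left to choose cut-points or methods after the data are known. The primary endpoint is not affected.

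**Working it through.** **1. The plan's own figures.** Section 10.2 rejects the null at 16 or more responders of 23. Exact binomial tails give P(X ≥ 16 | n=23, p=0.5) = 0.0466 and P(X ≥ 16 | n=23, p=0.75) = 0.8037, matching the stated 0.047 and 80.4%. Attrition: 23/0.8 = 28.75, so 29; 40/0.8 = 50. The increase is 40 − 23 = 17 evaluable patients. All of this concerns the primary endpoint; no power or precision figure is given for any secondary endpoint or biomarker.

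**2. Endpoint against analysis.**

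| Outcome | Defined as | Test of change in 10.4.3 |
|---|---|---|
| WOMAC, VAS | scores | signed-rank |
| Pain medication | frequency over 30 days (3.2) | McNemar, yes/no |
| Injections, physical therapy | frequency over 12 months (3.2) | McNemar, yes/no |
| MRI features | present or absent | McNemar, suitable |
| Technical success, adverse events | proportions, no baseline | none needed |
| EQ-5D-5L | scale (4.2.2 item 6) | not named |
| Biomarkers | levels (7.2.1, 10.5) | not named |

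**3. Laboratory timing.** The Schedule of Activities has visits at 1 day, 1, 3 and 12 months, and an optional one at 18–48 months. Blood and urine are drawn at baseline, 1, 3 and 12 months and at the optional visit if attended in person. Item 12 lists 1, 3 and 6 months and the final visit. Six months has no visit; twelve months has samples but no endpoint.

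**4. What dichotomising would cost.** The documents give no effect size, SD, correlation or cut-point, so all of these are assumptions. Model: baseline X standard normal; follow-up Y = ρX + √(1−ρ²)·Z − δ, with Z standard normal. The SD of the change is √(2(1−ρ)), which is 1 at ρ=0.5, so δ=0.5 is also half an SD of the change. Tests are two-sided at 5%: signed-rank on X−Y, and exact McNemar after a cut at c.

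For δ=0.5, the expected net number of 40 patients crossing the cut is 40 × [P(X>c) − P(Y>c)]:

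- c=0 (median): 40 × (0.500 − 0.309) = 7.7
- c=0.8: 40 × (0.212 − 0.097) = 4.6
- c=1: 40 × (0.159 − 0.067) = 3.7

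McNemar works from these few patients. Simulated power (2,000 or more replicates, ρ=0.5):

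| n, δ | Signed-rank | McNemar, median cut | McNemar, cut at 0.8 SD |
|---|---|---|---|
| 40, 0.5 | about 0.85 | about 0.45 | about 0.24 |
| 40, 0.4 | about 0.67 | about 0.29 | about 0.16 |
| 23, 0.5 | about 0.60 | – | – |

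Over ρ from 0.3 to 0.7 with δ=0.5 and n=40, signed-rank power is 0.73 to 0.97. McNemar power is 0.40 to 0.53 with a median cut and 0.15 to 0.17 with a cut at 1 SD. Signed-rank at n=23 is 0.45 to 0.83, above McNemar at n=40 for the same correlation, though narrowly at ρ=0.3 (0.45–0.48 against 0.40).

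**5. Sparse counts.** Normal-data figures do not carry over to injections or therapy sessions. With independent Poisson counts and n=40 (also assumed), a mean falling from 0.5 to 0.2 gives about 0.61 for signed-rank against 0.47 for McNemar on any/none. A mean falling from 1.0 to 0.5 gives about 0.73 against 0.48.

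**6. Multiplicity.** Section 7.2.1 lists 7 inflammatory, 3 pain and 2 collagen-degradation markers, and 2 + 1 + 5 = 8 starred optional ones: 20 in all. At 1, 3 and 12 months that is 20 × 3 = 60 tests, with 60 × 0.05 = 3 nominal positives expected if no marker changes.

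**The case against.** A reader might infer that every secondary measure other than WOMAC and VAS, including EQ-5D-5L and the biomarkers, is to be dichotomised. The documents do not support that. The McNemar clause reads most naturally as covering the remaining items in the 10.4.3 list, where neither appears, and no cut-point exists for either. Their defect is omission. McNemar also suits the MRI features, and technical success and adverse events are plain proportions with no baseline.

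A reader might also conclude that the plan throws away more information than the 17 extra patients add. That holds only if the biomarkers are dichotomised and only under the assumptions above, so it cannot be stated as a fact about this plan.

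Further points in the plan's favour stand. A point estimate and 95% CI for change are promised for every secondary outcome, so the loss from dichotomising falls on the tests. The daily-use coding is only an example. The exclusion of ipsilateral injection in the previous 3 months (section 5.2) may leave baseline injection counts low, where the loss is smaller. Section 7.2.1 associates the biomarker samples with exploratory analysis. These are secondary endpoints of a single-arm pilot.

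These points limit the size of the concern but do not remove it. The frequency objectives are still tested as yes/no, two endpoints still lack a test, and the promised interval has no scale or method. Item 12 is wrong as written without any assumption.

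**Conclusion.** The point holds in three parts. First, section 10.4.3 tests as yes/no three outcomes that section 3.2 defines as frequencies. Second, it names no test for EQ-5D-5L or for the biomarkers, whose change is one of two stated reasons for the larger sample. Third, section 4.2.2 item 12 names a time point with no visit and leaves out one with samples.

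The first two parts and the third can be read directly from the text. The power loss cannot: the fall from about 0.85 to about 0.45 or 0.24 depends on an assumed 0.5 SD shift, correlation 0.5, normal data and chosen cuts. It illustrates what dichotomising a continuous outcome would cost and does not estimate the loss in this trial. For sparse injection or therapy counts the gap is smaller, though in the same direction. The plan should be changed, but the primary conclusion does not depend on it.

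**What to change.** In section 10.4.3:

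- Analyse medication, injection and therapy frequencies with the paired Wilcoxon signed-rank test and a Hodges-Lehmann estimate with 95% CI. Use ordinal categories if the case report form does not record counts. Section 7.1.1 asks for injection and therapy frequency but only a medication history for the last month, and the forms are attachments that are not available here.
- Name EQ-5D-5L and each biomarker (log scale) with the same paired analysis, so that the promised estimate and interval have a stated scale and method.
- Keep McNemar for truly binary items, such as MRI features or any opioid use.
- Label the biomarker tests exploratory, or adjust them for multiplicity.

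In section 4.2.2 item 12, change 6 months to 12 months to match section 7.2.1 and the Schedule of Activities.

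The cost is wording and slightly more analysis work, with no new visits or samples. The real downside is more tests, about 60 for the biomarkers alone, which is why the exploratory or multiplicity statement is needed. The 8 optional markers may also have fewer than 40 patients.
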